### 8.2.1.4 *Vaccination History*

Obtain the participant's vaccination history by interviewing the participant and/or review of the participant's vaccination records.

History of following vaccine administration should be recorded in eCRF:

- Any vaccine administered up to 1 year before study vaccine administration (if possible, with the date of vaccination)
- Live Zoster vaccine administration (if possible, with the date of vaccination)
- COVID-19 vaccine administration (if possible, with the date of vaccination; this information should be collected even if administration was >1 year)

#### **8.2.1.5    *Targeted Physical Examinations***

History directed/targeted physical examination will be performed for each participant on Visit 1 (Day 1). If the investigator determines that the participant's health on the day of study intervention administration temporarily precludes dosing, the visit will be rescheduled. Refer to the [Section 5.6](#) for the list of criteria for temporary delay of study intervention administration.

Treatment of any abnormality observed during this examination has to be performed according to local medical practice outside this study or by referral to an appropriate health care provider.

Physical examination at each study visit after the study intervention administration visit, will be performed only if the participant/participant's caregiver indicates during questioning that there might be some underlying pathology(ies) or if deemed necessary by the investigator or delegate.

#### **8.2.1.6    *Body Temperature***

The body temperature of each participant needs to be measured prior to any study intervention administration and recorded in the eCRF. The route for measuring temperature can be oral or axillary. If the participant has fever (fever is defined as temperature  $\geq 38.0^{\circ}\text{C}$  ( $100.4^{\circ}\text{F}$ ) regardless the location of measurement) on the day of vaccination, the vaccination visit will be rescheduled within the allowed interval for this visit.

### **8.2.2    Safety Contact at 6 Months Post-Last Vaccination**

Six months after the last dose of study vaccine (i.e., Month 8), each participant should be contacted to check if he/she has experienced any SAEs or any pIMDs since last study intervention administration, and to collect information on concomitant medications/vaccinations and pregnancy information.

Multiple formats can be proposed by the site staff to organize these contacts. This contact may be done via email, text message, fax, or phone call for example. The most appropriate format should be agreed between site staff and the study participant.

Text messages, email, and fax may be used as a screening to check if the participant has anything to report. If the participant answers "Yes" for at least one of the items of interest, a phone call must be done to get the details on the event(s).

Data collected via phone calls and text messages will have to be recorded in source documents. E-mails and faxes can be archived in source documents. Receipt of the message must be confirmed by the participant or caregiver, as applicable.

### **8.2.3 Clinical Safety Laboratory Tests**

No clinical safety laboratory tests are scheduled for this study.

## **8.3 Adverse Events, Serious Adverse Events, and Other Safety Reporting**

Solicited and unsolicited AEs, SAEs and other safety reporting (pIMDs and pregnancy) are to be reported as indicated in this protocol; Refer to [Table 1](#) (Co-ad group) and [Table 2](#) (Control group). The administration site solicited AEs that will be collected are erythema, pain, and swelling. The systemic solicited AEs that will be collected are arthralgia, fatigue, fever, headache, myalgia, shivering/chills and gastrointestinal symptoms (nausea, vomiting, diarrhea and/or abdominal pain).

Safety monitoring is specified in [Figure 1](#) and in the endpoints ([Section 3.0](#)).

The definitions of AEs and SAEs can be found in [Appendix 3](#).

Adverse events will be reported by the participant (or, when appropriate, by a caregiver).

The investigator and any qualified designees are responsible for detecting, documenting, and recording events that meet the definition of an AE or SAE and remain responsible for following up on AEs that are serious, considered related to the study intervention or study procedures, or that caused the participant to discontinue the study/study intervention (see [Section 7.0](#)).

The method of recording, evaluating, and assessing causality of AEs and SAEs and the procedures for completing and transmitting SAE reports are provided in [Appendix 3](#).

### **8.3.1 Time Period and Frequency for Collecting AE, SAE, and Other Safety Information**

All SAEs and pIMDs will be collected from the start of study intervention until 6 months after the last administration of study interventions at the time points specified in the SoA ([Section 1.3](#)). All pregnancies beginning after the administration of the first study intervention until end of study will be collected at the time points specified in the SoA ([Section 1.3](#)).

SAEs assessed as related to study participation (e.g., study intervention, protocol-mandated procedures, invasive tests, or change in existing therapy) or related to a GSK product (non-investigational medicinal product) will be recorded from the time a participant consents to participate in the study until EoS.

All AEs/SAEs/pIMDs/pregnancies leading to withdrawal from the study will be collected and recorded from the time of the first receipt of study intervention until EoS.

All AEs will be collected in the timeframe showed in [Table 13](#) and [Table 14](#).

The investigator or designee will record and immediately report all SAEs to IQVIA via the Expedited AE Reporting Form. Reporting should, under no circumstances, occur later than 24 hours after the investigator becomes aware of an SAE, as indicated in [Appendix 3](#). The investigator will submit any updated SAE data to IQVIA within 24 hours of it being available.

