Sample collected at Day 31 will be used for the post-vaccination RSV antibodies-related testing.

Sample collected at Day 91 will be used for the post-vaccination HZ/su antibodies-related testing.

The route for measuring temperature can be oral or axillary. Fever is defined as temperature  $\geq 38.0^{\circ}\text{C}/100.4^{\circ}\text{F}$ , regardless of the location of measurement.

Designated site staff should review the eDiary frequently during the active event collection period to assess participant/caregiver compliance and monitor reported events.

SAEs related to study participation, or to a concurrent GSK medication/vaccine should be collected from the time of consent obtained (prior to study intervention) up to study end.

At Visits 1 and 3 (Co-ad group), pregnancy information must be recorded prior to study intervention administration. Pregnancies will be followed as described in [Section 10.4.3](#).

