## 5.5 Screen Failures

A screen failure occurs when a participant who has consented to participate in the clinical study is not subsequently randomized to study intervention/entered in the study.

Limited data for screening failures (including reason for screening failure and any serious adverse events (SAEs) related to study participation, or to a concurrent GSK medication/vaccine from the time of consent obtained) will be collected and reported in the electronic case report form (eCRF).

Individuals who do not meet the criteria for participation in this study (screen failure) but at some point, in the future are expected to meet the eligibility criteria may be rescreened. Individuals who are rescreened will be assigned a new participant number and will undergo the informed consent process, and then restart a new screening phase.

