**Table 13 Timeframes for Collection and Reporting of Safety Information for the Co-ad Group**

Event	Visit 1	Visit 1				Visit 2	Visit 3			Visit 4	Contact 1
	Day 1	Day 1	Day 7	Day 8 	Day 30	Day 31	Day 61	Day 67	Day 90	Day 91	Month 8 
	Pre-Dose 	RSV + HZ/su vacc.					HZ/su vacc.				End of Study
Administration site and systemic solicited events (eDiary)											
Unsolicited AEs											
All SAEs											
All pIMDs											
Recording of pregnancies 											
SAEs related to study participation or concurrent GSK medication/vaccine											
AEs/SAEs leading to withdrawal from the study											
Intercurrent medical conditions											

Abbreviations: AE=adverse event; eDiary=electronic diary; pIMD=potential immune-mediated disease; SAE=serious adverse event;

Vacc.=vaccination.

shading indicates applicable timeframe for reporting of safety information.

shading indicates reporting timeframe applicable if solicited symptoms persist after 7 days.

Collection of SAEs related to study participation or GSK medication/vaccine starts as of informed consent (prior to study intervention administration).

Day 8 Remote Contact for the sentinel group only for both groups.

Six months after the last study vaccination.

At Visits 1 and 3 (Co-ad group), pregnancy information must be recorded prior to study intervention administration. Pregnancies that occur post first study intervention will be followed as described in [Section 10.4.3](#).

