#### **10.3.5.1 Time Period for Collecting and Recording AEs, SAEs, pIMDs, Pregnancies**

Time Period for Collecting and Recording AEs, SAEs, and pIMDs

• All solicited events that occur during 7 days following administration of the dose of study intervention (Day 1 to Day 7) must be recorded into the eDiary, irrespective of intensity. All other AEs occurring within this time frame should be recorded onto/into the appropriate section of the eCRF, irrespective of their intensity or whether or not they are considered related to the study intervention.

• All unsolicited AEs that occur during 30 days following administration of each dose/the dose of study intervention must be recorded onto/into the appropriate section of the eCRF, irrespective of their intensity or whether or not they are considered related to the study intervention.

• SAEs related to study participation or concurrent GSK medication/vaccine will be collected from the time a participant consents to participate in the study until the participant is discharged from the study.

• All other SAEs and pIMDs will be collected from the start of study intervention until 6 months after the last administration of study interventions at the time points specified in the SoA (Section 1.3).

• Pregnancies will be collected from the first administration of study intervention until end of study as described in Section 10.4.3.

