## **11. GENERAL MEDICAL / VACCINATION HISTORY AND EXAMINATIONS**

Information both on Medical / Vaccination History will be summarized for the ES by group and will be reported, along with pregnancies, as tabular listing based on SCR respectively.

- Medical History will be coded using Medical Dictionary for Regulatory Activities (MedDRA) central coding dictionary, Version 25.1 or higher.
- Data captured on the “Medical History” page of the eCRF will be presented by MedDRA System Organ Class (SOC), High Level Terms (HLT) and Preferred Term (PT). Medical occurrences that begin before the start of study intervention but after obtaining informed consent will be recorded on the Medical History section of the eCRF, not the AE section.

A listing of medical / vaccination history data will be provided.

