### **16.1.5. Serious Adverse Events**

Analysis of serious adverse events (SAEs) from first vaccination (Visit 1, Day 1) up to 6 months post-last vaccination, the reporting period will start at vaccination and will end at approximately 6 months post-last vaccination (i.e., day of last vaccination+[180-210]).

SAEs will be summarized and listed as:

[figure not shown]
- The number and percentage of participants, with exact 95% CIs, with at least one report of SAE with onset after each vaccine administration up to study end (i.e. 6 months post-last vaccination). This summary will be repeated for:
  - Causally related SAEs
  - Fatal SAEs
- All SAEs will be included in a listing.
- All SAEs leading to study discontinuation or vaccine discontinuation at any point from first vaccination up to study end will be included in a listing and a tabulated listing.
- For web posting purposes, the number of occurrences and the number and percentage of participants with at least one SAE with onset after each vaccine administration up to study end (i.e. 6 months post-last vaccination) will be produced by SOC and PT. The same table will be produced for related SAE, fatal SAE and related fatal SAE.

Subgroup analysis will be created for the serious events up to study end (6 months after last dose) split by age category, race, ethnicity and gender.

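### SAP section 11 contradicts the protocol on study-related SAEs between consent and first dose, and the SAP does not settle whether those SAEs are listed

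*Protocol*

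**What the plan says.** The protocol treats one class of SAE differently from the rest. SAEs in general are collected from the start of study intervention. SAEs related to study participation or to a concurrent GSK medication or vaccine are collected from consent.

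- Section 8.3.1 says they "will be recorded from the time a participant consents to participate in the study until EoS".
- Footnote 10 of Table 1 says they "should be collected from the time of consent obtained (prior to study intervention) up to study end". Footnote 11 of Table 2 gives the same rule for the Control group.
- Footnote 1 of Tables 13 and 14 also starts this collection at informed consent.
- Section 10.3.5.1 says they "will be collected from the time a participant consents to participate in the study until the participant is discharged from the study".
- Section 5.5 extends the rule to people who are never randomized: "Limited data for screening failures (including reason for screening failure and any serious adverse events (SAEs) related to study participation", from consent, go into the eCRF.

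The SAP, in section 11, sends medical occurrences that begin before study intervention but "after obtaining informed consent will be recorded on the Medical History section of the eCRF, not the AE section". Section 16.1.5 starts the SAE reporting period at first vaccination but also says "All SAEs will be included in a listing". Section 16 puts all safety outputs on the Exposed Set. Section 6 puts listings of all collected data on the Screened Set unless otherwise specified.

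**The concern.** The protocol's early start for study-related SAEs is deliberate: it is repeated in six places and has its own row in both schedules of activities. Its purpose is to capture harm caused by the study itself, including harm before any vaccine is given. A SAP rule that places everything in the same interval under Medical History would turn such an event into a baseline condition.

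At stake is whether the safety listings are complete for a category of SAE that the protocol requires to be collected. If the SAP rule were followed literally, a serious injury caused by a study procedure could be tabulated alongside pre-existing conditions. No estimate, hypothesis test or group comparison is involved.

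**Working it through.** No arithmetic applies. The check sets the passages side by side.

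**1. Can such an event occur before dosing?** Yes. Section 8.3.1 defines the class broadly: "SAEs assessed as related to study participation (e.g., study intervention, protocol-mandated procedures, invasive tests, or change in existing therapy"). The Visit 1 blood sample is taken before vaccination (Table 12). Table 5 names fainting around a blood draw as a risk of study procedures. Under section 5.6, dosing may be postponed after the Visit 1 blood has been taken, and the sample need not be repeated, so the interval between procedure and first dose can be longer than one visit.

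**2. Where do the two recording rules collide?** An event must meet three conditions: it is serious; it is related to study participation or to a concurrent GSK product; and it begins after consent and before the first dose. The protocol then makes it an SAE record, while SAP section 11 makes it a Medical History record and explicitly not an AE record. For other occurrences in that interval the SAP rule fits the protocol, which defines an AE by its timing relative to study intervention (section 10.3.1) and puts conditions present before intervention into medical history (section 8.2.1.3). The collision is narrow but direct.

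**3. Would the event be listed?** SAP provisions that point to inclusion:
- Section 16.1.5 promises a listing of all SAEs.
- Section 6 defaults listings to the Screened Set.
- Appendix 2 uses a flag for AE onset before or after vaccination to impute partial dates, so the AE data are expected to hold some pre-vaccination onsets.

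SAP provisions that point to exclusion:
- Section 11 keeps the event out of the AE section.
- Section 16.1.5 starts the SAE period at first vaccination.
- Section 16 restricts all safety outputs to the Exposed Set.

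**4. Apply this to two participants, each with the event correctly recorded as an SAE under the protocol.**
- *Later dosed.* The participant is in the Exposed Set. The event is listed only if the promise to list all SAEs overrides the vaccination start of the reporting period. The SAP does not say which prevails.
- *Never dosed, for example a screen failure.* The participant is outside the Exposed Set. The event is listed only if the Screened Set default in section 6 overrides section 16. But section 6 yields wherever something else is specified, and section 16 specifies the Exposed Set for safety outputs. Exclusion is the more natural reading, although section 5.5 of the protocol requires the event to be collected.

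**5. Does the SAE percentage move?** No. The secondary endpoint in protocol section 3.0 counts SAEs after vaccine administration on Day 1, so pre-dose events are outside it under either rule.

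**The case against.** The strongest reply is that the SAP does not tell sites where to record events. Its introduction limits it to presentation and analysis. The protocol governs recording: both schedules of activities mark these SAEs at Visit 1 as requiring eCRF documentation, and section 10.3.6 requires electronic entry of SAEs within 24 hours. This stands. A reader might infer from SAP section 11 that every pre-dose study-related SAE would be misfiled as medical history. The documents do not support that, because nothing suggests that sites would follow a sentence in a SAP over repeated protocol instructions. Expedited reporting is unaffected.

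A reader might also infer that these SAEs are certain to be missing from the SAE listing. That is not established either, given the promise to list all SAEs, the Screened Set default and the pre-vaccination onset flag. The output templates mentioned in SAP section 8 might settle it, but they are not part of the documents reviewed. What can be said is that the SAP text is inconsistent.

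Nor should much be made of SAP section 3.3, which declares no changes. Its heading concerns protocol-defined analyses, and the protocol defines no analysis of pre-dose SAEs.

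What remains after these concessions is the direct contradiction on recording, the unresolved listing rule, and the Exposed Set restriction for participants who are never dosed.

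**Conclusion.** SAP section 11 is wrong as written against the protocol, and SAP 16/16.1.5 gives no assurance that study-related or GSK-product-related SAEs before the first dose will be listed, least of all for participants never dosed. This is a minor reconciliation of safety-listing completeness. It does not affect the primary conclusions, the SAE percentages or expedited reporting.

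The documents give no expected count of such events. That few are likely is a judgment from the design: there is no separate screening visit (protocol section 4.1.1), so consent, blood draw and dosing normally share Visit 1. Delayed dosing and screen failures are the situations in which the gap is most likely to matter. The conclusion assumes that the SAP text stands without clarification in its templates.

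**What to change.** Two changes are needed, because correcting section 11 alone would leave the vaccination start and the Exposed Set restriction in place.

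1. In SAP section 11, except SAEs related to study participation or to a concurrent GSK medication/vaccine from the Medical History rule, and state that they are recorded as SAEs from informed consent under protocol section 8.3.1.
2. In SAP sections 16 and 16.1.5, state that the all-SAE listing is produced on the Screened Set, as an exception to the Exposed Set rule, and includes these SAEs from consent. Flag them as pre-vaccination and exclude them from the post-vaccination percentages.

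The cost is two sentences in the SAP and one flag in one listing. The protocol already requires the data to be collected, so nothing new is needed from sites.

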**Table 13 Timeframes for Collection and Reporting of Safety Information for the Co-ad Group**

Event	Visit 1	Visit 1				Visit 2	Visit 3			Visit 4	Contact 1
	Day 1	Day 1	Day 7	Day 8 	Day 30	Day 31	Day 61	Day 67	Day 90	Day 91	Month 8 
	Pre-Dose 	RSV + HZ/su vacc.					HZ/su vacc.				End of Study
Administration site and systemic solicited events (eDiary)											
Unsolicited AEs											
All SAEs											
All pIMDs											
Recording of pregnancies 											
SAEs related to study participation or concurrent GSK medication/vaccine											
AEs/SAEs leading to withdrawal from the study											
Intercurrent medical conditions											

Abbreviations: AE=adverse event; eDiary=electronic diary; pIMD=potential immune-mediated disease; SAE=serious adverse event;

Vacc.=vaccination.

shading indicates applicable timeframe for reporting of safety information.

shading indicates reporting timeframe applicable if solicited symptoms persist after 7 days.

Collection of SAEs related to study participation or GSK medication/vaccine starts as of informed consent (prior to study intervention administration).

Day 8 Remote Contact for the sentinel group only for both groups.

Six months after the last study vaccination.

At Visits 1 and 3 (Co-ad group), pregnancy information must be recorded prior to study intervention administration. Pregnancies that occur post first study intervention will be followed as described in [Section 10.4.3](#).

**Table 14 Timeframes for Collection and Reporting of Safety Information for the Control Group**

Event	Visit 1	Visit 1				Visit 2			Visit 3			Visit 4	Contact 1
	Day 1	Day 1	Day 7	Day 8 	Day 30	Day 31	Day 37	Day 60	Day 61	Day 67	Day 90	Day 91	Month 8 
	Pre-Dose 	HZ/su vacc.				RSV vacc.			HZ/su vacc.				End of Study
Administration site and systemic solicited													
Unsolicited AEs													
All SAEs													
All pIMDs													
Recording of pregnancies 													
SAEs related to study participation or													
AEs/SAEs leading to withdrawal from the													
Intercurrent medical conditions													

Abbreviations: AE=adverse event; eDiary=electronic diary; SAE=serious adverse event; pIMD=potential immune-mediated disease; Vacc.=vaccination.

shading indicates applicable timeframe for reporting of safety information.

shading indicates reporting timeframe applicable if solicited symptoms persist after 7 days.

 Collection of SAEs related to study participation or GSK medication/vaccines starts as of informed consent (prior to study intervention administration).

 Day 8 Remote Contact for the sentinel group only for both groups.

 Six months after the last study vaccination.

At Visits 1, 2, and 3 (Control group), pregnancy information must be recorded prior to study intervention administration. Pregnancies that occur post first study intervention will be followed as described in [Section 10.4.3](#).

A post-study AE/SAE is defined as any event that occurs outside of the AE/SAE reporting periods defined in [Table 13](#) and [Table 14](#). Investigators are not obligated to actively seek information on AEs or SAEs after conclusion of the study participation. However, if the investigator learns of any SAE, including a death, at any time after a participant has been discharged from the study, and he/she considers the event/cause of death to be reasonably related to the study intervention or study participation, the investigator must promptly notify IQVIA.

